8.4.3. Medication Errors

Other exposures to the investigational product under study may occur in clinical trial settings, such as medication errors.

| Safety Event | Recorded on the CRF | Reported on the CT SAE Report Form to Pfizer Safety Within 24 Hours of Awareness |
|---------------------|---|---|
| Medication errors | All (regardless of whether associated with an AE) | Only if associated with an SAE |

8.4.3.1. Medication Errors

Medication errors may result from the administration or consumption of the investigational product by the wrong subject, or at the wrong time, or at the wrong dosage strength.

Medication errors include:

- Medication errors involving subject exposure to the investigational product;
- Potential medication errors or uses outside of what is foreseen in the protocol that do or do not involve the participating subject.

Such medication errors occurring to a study participant are to be captured on the medication error page of the CRF, which is a specific version of the AE page.

In the event of a medication dosing error, the sponsor should be notified immediately.

Whether or not the medication error is accompanied by an AE, as determined by the investigator, the medication error is recorded on the medication error page of the CRF and, if applicable, any associated AE(s), serious and non-serious, are recorded on an AE page of the CRF.

Medication errors should be reported to Pfizer Safety within 24 hours on a CT SAE Report Form **only when associated with an SAE**.

9. DATA ANALYSIS/STATISTICAL METHODS

Detailed methodology for summary and statistical analyses of the data collected in this study is outlined here and further detailed in a Statistical Analysis Plan (SAP), which will be maintained by the sponsor. The SAP may modify what is outlined in the protocol where appropriate; however, any major modifications of the primary endpoint definitions or their analyses will also be reflected in a protocol amendment.

9.1. Sample Size Determination

Approximately, 8 subjects will be enrolled into each of the normal, mild, moderate, and severe renal impairment groups as described in [Section 3.1](#). The sample size is based on recommendations from the “Food and Drug Administration (FDA) Guidance for Industry - Pharmacokinetics in Patients with Impaired Renal Function-Study Design, Data Analysis, and Impact on Dosing and Labeling”.

Subjects who discontinue from the study before completing all assessments may be replaced at the discretion of the investigator and Sponsor to ensure 8 evaluable subjects in each of normal, mild, and moderate impairment groups (Groups A, B, and C) and at least 4 evaluable subjects in severe group (Group D).

9.2. Pharmacokinetic Analysis

The PK concentration population is defined as all subjects enrolled and treated and who have at least 1 lorlatinib concentration.

The PK parameter analysis population is defined as all subjects enrolled and treated who have at least 1 of the PK parameters of primary interest.

Subjects are considered PK evaluable if all PK concentrations are available or at the discretion of the Sponsor Clinical Pharmacologist.

9.2.1. Derivation of Pharmacokinetic Parameters Prior to Analysis

Pharmacokinetic parameters following single dose administration will be derived from the concentration-time profile as follows:

Table 6. Derivation of Pharmacokinetic Parameters

| Parameters | Definition | Method of Determination |
|--------------|---|---|
| AUC_{last} | Area under the plasma concentration time curve from time 0 to the time of the last quantifiable concentration | Linear-log trapezoidal method. |
| AUC_{inf} | Area under the plasma concentration-time curve from time 0 extrapolated to time infinity | $AUC_{inf} = AUC_{last} + (C_{last}/k_{el})$ C_{last} , plasma concentration at the last quantifiable time point estimated from the log-linear regression analysis. k_{el} , terminal elimination phase rate constant estimated by linear regression based on the observations justified to describe the terminal phase on log-linear concentration-time profile. |
| C_{max} | peak or maximum observed plasma concentration | Observed directly from data |
| T_{max} | Time to C_{max} | Observed directly from data as time of first occurrence |
| $t_{1/2}$ | Terminal plasma elimination half-life | $\ln(2)/k_{el}$ |
| CL/F | Apparent clearance after oral dose | $Dose/AUC_{inf}$ after oral dose |
| V_z/F | apparent oral volume of distribution | $Dose/(AUC_{inf} \times k_{el})$ after oral dose |
| CL_R | Renal clearance | Ae/AUC_{last} |

Table 6. Derivation of Pharmacokinetic Parameters

| Parameters | Definition | Method of Determination |
|-----------------------|---|---|
| Ae | Cumulative amount of drug recovered unchanged in the urine, from zero to time 120 hours post-dose | Sum of [urine concentration \times sample volume ^a] for each collection interval. |
| Ae% | Cumulative amount of drug recovered unchanged in the urine, from zero to time 120 hours post-dose, expressed as fraction of administered dose | Ae/Dose*100% |
| MRC _{max} | Metabolite(s) to parent ratio for C _{max} | (C _{max} /MW) _{metabolite} /(C _{max} /MW) _{parent} |
| MRAUC _{last} | metabolite(s) to parent ratio for AUC _{last} | (AUC _{last} /MW) _{metabolite} /(AUC _{last} /MW) _{parent} |
| MRAUC _{inf} | metabolite(s) to parent ratio for AUC _{inf} | (AUC _{inf} /MW) _{metabolite} /(AUC _{inf} /MW) _{parent} |

MW: Molecular Weight

^a Sample volume = (urine weight in g/1.020), where 1.020 g/mL is the approximate specific gravity of urine.

Actual PK sampling times will be used in the derivation of PK parameters. In the case of actual PK sampling times are not available, nominal PK sampling time will be used in the derivation of PK parameters.

9.2.2. Statistical Methods

Analysis of variance (ANOVA) will be used to compare the natural log transformed AUC_{inf} (if data permit), AUC_{last} and C_{max} between the normal renal function group and each of the renal impairment groups. Point estimates and associated 90% confidence intervals (CIs) for the difference of each comparison will be estimated and exponentiated to provide geometric mean ratios and associated 90% CIs.

Regression analysis will be conducted to characterize the relationship between renal function and PK parameter CL/F. Both CL_{cr} calculated from the C-G formula and eGFR obtained from the MDRD equation on Day -1 will be used in regression analysis. Analysis results will include estimates of parameters for the chosen model as well as measures of precision such as CI or standard errors.

PK parameters AUC_{inf}, C_{max}, AUC_{last}, time for C_{max} (T_{max}), terminal plasma elimination half-life (t_{1/2}), CL/F, CL_R, V_z/F, cumulative amount of drug recovered unchanged in the urine, from zero to time 120 hours post-dose (Ae), cumulative amount of drug recovered unchanged in the urine, from zero to time 120 hours post-dose, expressed as fraction of administered dose (Ae%), will be summarized descriptively by analyte (eg, lorlatinib and its metabolite(s)) and renal function group. Metabolite(s) to parent ratio for C_{max} (MRC_{max}), metabolite(s) to parent ratio for AUC_{last} (MRAUC_{last}), and metabolite(s) to parent ratio for AUC_{inf} (MRAUC_{inf}) will also be summarized descriptively by renal function group.

For AUC_{inf}, AUC_{last} and C_{max}, box-whisker plots of the parameters will be plotted by analyte and renal function group. Individual concentrations will be listed and summarized descriptively by group and PK sampling time. Individual subject and summary profiles (means and medians) of the concentration-time data will be plotted across different groups.

For summary statistics and summary plots by renal function group and sampling time, the nominal PK sampling time will be used; for individual subject plots by time, the actual PK sampling time will be used.

9.3. Analysis of Other Endpoints

Pharmacogenomic and biomarker data will be collected and retained for future analyses, but may not be analyzed, specifically, for this study.

9.4. Safety Analysis

AEs, ECGs, BP, pulse rate, and safety laboratory data will be reviewed and summarized on an ongoing basis during the study to evaluate the safety of subjects. Any clinical laboratory, ECG, BP, and pulse rate abnormalities of potential clinical concern will be described. Safety data will be presented in tabular and/or graphical format and summarized descriptively, where appropriate.

Medical history and physical examination and neurological examination information, as applicable, collected during the course of the study will be considered source data and will not be required to be reported, unless otherwise noted. However, any untoward findings identified on physical and/or neurological examinations conducted during the active collection period will be captured as AEs, if those findings meet the definition of an AE. Data collected at screening that are used for inclusion/exclusion criteria, such as laboratory data, ECGs, and vital signs, will be considered source data, and will not be required to be reported, unless otherwise noted. Demographic data collected at screening will be reported.

9.4.1. Electrocardiogram Analysis

Changes from baseline for the ECG parameters QT interval, heart rate, QTc interval, PR interval, and QRS interval will be summarized by treatment and time.

The number (%) of subjects with maximum post-dose QTc values and maximum increases from baseline in the following categories will be tabulated by treatment:

Table 7. Safety QTc Assessment

| | Borderline (msec) | Prolonged (msec) |
|-----------------|-------------------|------------------|
| Absolute value | -- | ≥480 |
| Absolute change | 30-<60 | ≥60 |

In addition, the number of subjects with corrected and uncorrected QT values ≥500 msec will be summarized.

The number (%) of subjects with maximum post-dose PR interval values, maximum increases from baseline and second degree atrioventricular block (AVB) type 2 or higher in the following categories will be tabulated by renal function group ([Table 8](#)):

Table 8. Safety PR Interval

| | msec |
|---|----------------------|
| Absolute Value | ≥ 200 - < 220 |
| | ≥ 220 - < 240 |
| | ≥ 240 - < 260 |
| | ≥ 260 |
| Absolute Change | $40 - < 60$ |
| | $60 - < 80$ |
| | ≥ 80 |
| Relative Change from baseline | $> 25\%$ |
| Second-degree AVB type 2 or higher ^a | |

a. Second degree block type 2 or higher would be determined by the ECG machine and confirmed by a physician.

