1.3.1.1.5. Study B7461008

Study B7461008 is a completed Phase 1 study in 24 healthy volunteers, designed to evaluate the effect of rabeprazole and food on the pharmacokinetics of lorlatinib and to assess the relative bioavailability (BA) of an oral solution of lorlatinib to the tablet formulation of lorlatinib.

Results indicate that a high fat meal has no effect on the systemic exposure of lorlatinib. Similarly, proton pump inhibitor (PPI) rabeprazole had only a marginal effect on the systemic exposure of lorlatinib. Based on these results, the current recommendation is that lorlatinib can be given without regard to food or any acid reducing agents such as PPIs or H₂-receptor antagonists.

In one healthy volunteer, the PR interval prolongation was associated with one episode of transient second degree atrioventricular (AV) block (Mobitz type 1; Wenkebach). Subsequently, retrospective review of patients in Study B7461001, found one patient with the PR interval prolongation that may have been associated with the progression of pre-existing AV block to complete heart block. When the complete heart block was identified, the patient was immediately evaluated and subsequently treated by placement of an implanted pacemaker.

In response to the observation of PR interval prolongation, data from all available human studies (approximately 100 patients in Study B7461001 and 45 in single dose healthy volunteer studies) were reviewed. Additional instances were identified of asymptomatic increases in the PR interval (>200 msec), usually most notable at the time of C_{max} (1-2 hours post-dose) in healthy volunteers. Of note, the subjects with a PR interval >200 msec were generally those with a baseline values at the upper end of the normal range.

The electrocardiogram (ECG) changes appear limited to the PR interval, with no impact on QRS or QT intervals. This impact on the PR interval is supported by preclinical animal studies, as described in the current IB.

Although isolated PR interval prolongation (first or second degree AV block) may not pose an immediate risk to patient safety, the potential for development of complete heart block warrants that future studies exclude patients with a baseline PR interval ≥ 220 msec, or 2nd or 3rd degree AV block (unless an implanted pacemaker is in place). Further, for the healthy volunteers in this study the upper limit of normal for PR interval will be defined as PR interval of 180 msec.

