7.1.4. Electrocardiogram

Triplicate 12-Lead ECGs should be collected at times specified in the **SCHEDULE OF ACTIVITIES** section of this protocol.

All scheduled ECGs should be performed after the subject has rested quietly for at least 10 minutes in a supine position.

Triplicate 12-lead ECGs will be obtained approximately 2 to 4 minutes apart; the average of the triplicate ECG measurements collected at pre-dose of Day 1 will serve as each subject's time-controlled baseline QTc value.

If the average of QTc values from the triplicate measurements remains above the threshold value (ie, is ≥ 45 msec from the baseline, or is ≥ 500 msec), then a single ECG must be repeated at least hourly until QTc values from 2 successive ECGs fall below the threshold value that triggered the repeat measurement.

If QTc values remain ≥ 500 msec (or ≥ 45 msec from the baseline) for greater than 4 hours (or sooner, at the discretion of the investigator), or QTc intervals get progressively longer, the subject should undergo continuous ECG monitoring. A cardiologist should be consulted if QTc intervals do not return to less than 500 msec (or to <45 msec above the baseline) after 8 hours of monitoring (or sooner, at the discretion of the investigator).

If subject develops new first degree block as defined by PR interval greater than 280 msec, if patient is found to have a second degree or higher AV block, or if patient has symptomatic bradycardia, patient should undergo continuous cardiac monitoring with 12-lead ECG taken every hour until PR interval returns to <220 msec, until AV block resolves or until symptoms resolve. If patient develops high degree AV block defined as second degree AV block, Mobitz II or third degree block, patient should be referred to a cardiologist for further evaluation.

In some cases, it may be appropriate to repeat abnormal ECGs to rule out improper lead placement as contributing to the ECG abnormality. It is important that leads are placed in the same positions each time in order to achieve precise ECG recordings. If a machine-read QTc value is prolonged, as defined above, repeat measurements may not be necessary if a qualified medical provider's interpretation determines that the QTc values are in the acceptable range.

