8.3.7. ECG Data

The baseline measurement is the last planned predose triplicate measurement.

The average of the replicate readings collected at each assessment time will be calculated prior to summarizing the data across subjects.

Baseline values and *changes from baseline for the ECG parameters QT interval, heart rate, QTcF interval, PR interval, and QRS interval will be summarized by treatment group and time.*

The number (%) of subjects with maximum post-dose QTc values and maximum increases from baseline in the following categories will be tabulated by treatment:

	Borderline (msec)	Prolonged (msec)
Absolute value	--	≥ 480
Absolute change	30-<60	≥ 60

In addition, the number of subjects with corrected and uncorrected QT values ≥ 500 msec will be summarized.

The number (%) of subjects with maximum post-dose PR interval values, maximum increases from baseline and second degree atrioventricular block (AVB) type 2 or higher in the following categories will be tabulated by renal function group as below:

	Msec
Absolute Value	$\geq 200 - < 220$
	$\geq 220 - < 240$
	$\geq 240 - < 260$
	≥ 260
Absolute Change	$40 - < 60$
	$60 - < 80$
	≥ 80
Relative Change from baseline	$> 25\%$
Second-degree AVB type 2 or higher^a	

^a: Second degree block type 2 or higher would be determined by the ECG machine and confirmed by a physician.

These data will be listed in accordance with the sponsor reporting standards.

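### The only AV-block row in the ECG safety table starts at second-degree type 2, so it does not count Mobitz type 1, the second-degree block already reported in a lorlatinib healthy volunteer

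*Protocol*

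**What the plan says.** Protocol 9.4.1 plans counts by renal function group of maximum post-dose PR values, "maximum increases from baseline and second degree atrioventricular block (AVB) type 2 or higher in the following categories". The categories stand in Table 8, and SAP 8.3.7 repeats them. Each table has several PR bands and a single AV-block row, which begins at second-degree type 2. The footnote, the same in both documents, says how that row is filled: "Second degree block type 2 or higher would be determined by the ECG machine and confirmed by a physician".

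Protocol 1.3.1.1.5 describes the safety signal behind these rows. In one healthy volunteer in Study B7461008, PR prolongation was "associated with one episode of transient second degree atrioventricular (AV) block (Mobitz type 1; Wenkebach"). A retrospective review then found one patient in Study B7461001 whose PR prolongation "may have been associated with the progression of pre-existing AV block to complete heart block". The wider review covered about 100 patients and "45 in single dose healthy volunteer studies". It concluded that the ECG effect appears confined to the PR interval.

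Protocol 7.1.4 calls for continuous cardiac monitoring with hourly ECGs in several situations, among them "if patient is found to have a second degree or higher AV block". It reserves cardiology referral for "high degree AV block defined as second degree AV block, Mobitz II or third degree block".

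**The concern.** AV conduction is the ECG signal the protocol attributes to lorlatinib, and ECGs are among the secondary endpoints. The subjects here are non-cancer subjects given a single dose, so the healthy-volunteer event is the closest precedent. The tabulated class is narrower than the class the protocol acts on, and the gap between the two is type 1 block.

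What is at stake is how clearly the ECG table answers its own question. The population PK analysis in Protocol 1.4 found median clearance 18% and 26% lower in mild and moderate impairment, and the PR increases in healthy volunteers were usually most notable near Cmax. Whether conduction events gather in the more impaired groups is therefore a natural question for a table split by renal function. As written, the table cannot answer it for type 1 block.

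**Working it through.** The plan states no figure on this point, so the main check is to follow each class of block through the documents.

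| Class | Reported in Protocol 1.3.1.1.5 | Monitoring under Protocol 7.1.4 | Category in Table 8 and SAP 8.3.7 |
|---|---|---|---|
| PR prolongation, first degree | Yes, PR above 200 msec in healthy volunteers | If new and PR above 280 msec | Yes, PR bands from 200 msec and change bands |
| Second degree, type 1 | Yes, one healthy volunteer | Yes | **None** |
| Second degree, type 2 | Not reported | Yes, plus cardiology referral | Yes |
| Third degree | One patient, with pre-existing block | Yes, plus cardiology referral | Yes |

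Type 1 is the only class that has been reported before, triggers monitoring and has no category. A type 1 event therefore adds 0 to the AV-block row by definition.

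The PR bands do not fill the gap. They classify interval length, and SAP 8.3.7 averages the replicates at each time before summarizing. An averaged interval does not show a dropped beat.

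How often might this arise? The following is an illustration only, since the point does not depend on it.

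- Inputs: 1 type 1 event; 45 single-dose healthy volunteers reviewed (Protocol 1.3.1.1.5); about 32 evaluable subjects planned (Protocol 3.1).
- Rate: 1/45 = 2.2%, exact (Clopper-Pearson) 95% interval 0.06% to 11.8%.
- Expected events: 32 × 1/45 = 0.71.
- Chance of at least one: 1 − (44/45)^32 = 51%. At the interval ends it is about 2% and 98%.
- If Group D ends with 4 evaluable subjects (n = 28): 1 − (44/45)^28 = 47%.

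The result also depends on the denominator:

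- Using only the 24 volunteers of Study B7461008: 1 − (23/24)^32 = 74%. This is probably high, because it selects the study in which the event happened.
- Using the 95 volunteers in six studies from Protocol 1.4, and assuming no second case among them: 1 − (94/95)^32 = 29%.

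All of these assume that the earlier rate carries over. This study excludes baseline PR above 180 msec, and Protocol 1.3.1.1.5 says PR above 200 msec occurred generally in those with high-normal baselines, so the true chance should be lower. The documents give no figure for how much lower.

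**The case against.** The strongest reply is that the event would be reported anyway. A second-degree block leads to continuous monitoring under Protocol 7.1.4. Protocol 8.2.2 makes an abnormal finding an adverse event when it requires further diagnostic testing or intervention, or when the investigator or sponsor considers it one. SAP 8.3.4 reports adverse events by renal function group. Protocol 9.4 adds "Any clinical laboratory, ECG, BP, and pulse rate abnormalities of potential clinical concern will be described", and SAP 8.3.7 lists the ECG data. This largely stands. A reader might infer that a type 1 block would vanish from the report, and the documents do not support that. What remains is narrower. Adverse event counts depend on the term recorded, SAP 8.3.7 does not repeat the commitment to describe abnormalities, and neither document plans a physician-confirmed count of type 1 block by group.

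Second, the cut-off has a rationale. It matches the protocol's own high-degree class, and Protocol 1.3.1.1.5 names complete heart block as the main worry. This stands too. Different thresholds for monitoring and for tabulation are not a contradiction, and nothing here suggests the monitoring rule is wrong. Sub-rows would keep the severity distinction.

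Third, a zero in the row would be true as labelled. A reader might infer that the report would claim there was no AV block. It would not, because the label states where the count starts. Nor is the row a separate endpoint; it is one category within the ECG safety assessments.

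Fourth, the footnote does not bar confirmation of other blocks. That is correct; it simply does not provide for it.

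**Conclusion.** The point holds as a gap in tabulation. The ECG safety table in both documents has no count for second-degree type 1 block, the second-degree block reported in a lorlatinib healthy volunteer and part of the protocol's own monitoring trigger. This rests on the text alone.

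The consequence is modest. The event would probably appear among the adverse events by renal function group and in the ECG listings, so safety information is unlikely to be lost, and the primary PK analysis is untouched. That judgement assumes investigators record such a block as an adverse event, which Protocol 8.2.2 makes likely but does not guarantee by name.

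A reader might take 51% or 74% as the chance that the gap will matter. Neither should be relied on: both rest on one event, the interval around the 51% is about 2% to 98%, and the PR exclusion pulls the chance down. This is an inexpensive improvement to reporting, not an error that threatens the study's conclusions.

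**What to change.** In Protocol Table 8 and the matching table in SAP 8.3.7, replace the AV-block row with second-degree AVB, any type, or higher, by renal function group, with sub-rows for type 1, type 2 and third degree. Reword the footnote so that physician confirmation applies to every second-degree or higher block, and state that blocks found on the ECGs taken under Protocol 7.1.4 are included.

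The cost is one row expanded into a short block and one footnote, in each document. No ECGs, subjects or clinical rules change, since these blocks already have to be acted on when found. Protocol Section 9 allows the SAP to modify the outlined analyses and calls for an amendment only for major changes to the primary endpoint definitions or their analyses. The SAP could therefore carry the change first, with the protocol aligned at its next amendment.
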